7. TREATMENTS

The medical application was under the only responsibility of the patient's dentist.

The patients who will be documented in the study have been treated with OraVerse® within the last 3 months before contract signing.

8. STUDY PROCEDURES AND DATA COLLECTION

8.1 Data collected

At the dental office

Inclusion criteria will be collected.

 Information on patient age, classification of body weight, type of dental intervention, local anesthetic used (product and dose), dose of OraVerse® will be collected by the dentist.

8.2 Logistic aspects

Each of the participating dental centres and each of the dentists will be provided by Sanofi a file containing:

- NIS contract
- Protocol of the study
- Overview-page

- Facsimile
- For each documented patient (n=6)
 - CRF
- OraVerse® SmPC

The documents (CRF, overview-page) will be collected at dentist practice level and send in the enclosed envelope by mail to the CRO (Important: without name or address of the sender).

The enclosed Facsimile (containing number of documented patients (max 6), date, name, signature and personal seal of the dentist) will be faxed to NIS Management of Sanofi-Aventis Deutschland GmbH to [name] (No: [contact]).

9. MANAGEMENT OF DATA

9.1 Data collection, validation and data quality control at company level

Data will be collected using a paper CRF.

Data collection and validation procedures will be detailed in appropriate operational documents (Data Management Plan including a Data Validation Plan).

For quality assurance reasons, a duplicate data entry will be performed to assure the consistency of data.

9.2 Data quality control at site level

Based on the insights in the actual documentation practice gained at dentists' level with two recent studies on OraVerse®, we adjusted the current CRF to a standardized questionnaire with tickboxes for selection wherever possible. As a consequence of the anonymous study design, data quality control at site level can not be performed.

10. SAFETY REPORTING

Since this is a retrospective drug utilization study based on the analysis of preexisting data, only detection of safety signal is applicable. In case a safety signal will be identified during data analysis, this shall be immediately forwarded to Pharmacovigilance.

11. STATISTICAL METHODOLOGY

11.1 Analysis population(s)

 Patients treated with OraVerse® after local anaesthetic procedure by dentists within the last 3 months before contract signing

11.2 Analysis variables

- · patient age,
- classification of body weight (<15 kg, 15 30 kg, >30 kg, no classification possible)
- type of dental intervention,
- local anesthetic used (product and dose),
- dose of OraVerse[®]

11.2.1 Primary variables - criteria

The primary outcome will be the incidence of patients who "comply"/"not comply" with the recommendations in the SmPC regarding the following points:

- patient age
 - The extent to which OraVerse® has been used in children <6 years
- type of dental intervention
 - The extent to which OraVerse® has been used for indications other than recommended in the SmPC
- local anesthetic used (product and dose),
- dose of OraVerse[®]
 - The extent to which doses of OraVerse® has been used other than recommended in the SmPC (dose of OraVerse® depends on e.g. patient's age, class of body weight and dose of used local anesthetic)

11.3 Statistical methods

Descriptive statistics for all collected and derived data will be provided. For continuous data number of patients, mean, standard deviation, median, min, max, quartiles and appropriate other percentiles will be provided. For categorical data frequencies and percentages will be presented. For estimated parameters suitable 95% confidence intervals will be provided. All statistical analyses are exploratory in nature. All statistical analyses will be described in detail in a separate document (Statistical Analysis Plan (SAP)) prepared before data base closure.

11.4 Determination of sample size

With a sample size of 500 patients the following statistical precision for the estimated proportion of patients who are 'not comply'/'comply' with the doses and indications recommended in the SmPC can be reached: Assuming rates of not adherence/adherence to labelling of 3%/97% or 4%/96% or 5%/95%, the 2-sided 95% confidence intervals will be [1.5%; 4.5%]/[95.5%; 98.5%] or [2.3%; 5.7%]/[94.3%; 97.7%] or [3.1%; 6.9%]/[93.1%; 96.9%].

In general: when the sample size is 500, a two-sided 95.0 % confidence interval for a single proportion using the large sample normal approximation will extend 0.015 or 0.017 or 0.019 from the observed proportion for an expected proportion of 0.030 (or 0.97) or 0.04 (or 0.96) or 0.05 (or 0.95).

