6.3.2 Patient selection

Each selected dentist and who will have agreed to participate to the study should have included up to 6 patients who meet inclusion criteria (treatment with OraVerse® within the last 3 months before contract signing).

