13.3 Data protection

As defined and described in the RISK MANAGEMENT PLAN for Oraverse®, data collection will be completely anonymous. No backtracking will be possible, since the CRFs will be documented and evaluated without any identification attribute (no patient number, no site number). Therefore no informed consent of the patient is necessary.

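### The precision in section 11.4 treats 500 patients from about 100 dentists as independent, and the ban on site numbers in 13.3 leaves the design effect impossible to estimate from the data

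*Protocol*

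**What the plan says.** Section 11.4 bases the sample size on precision. The stated premise is "Assuming rates of not adherence/adherence to labelling of 3%/97% or 4%/96% or 5%/95"%, and the resulting limits are given as "the 2-sided 95% confidence intervals will be [1.5%; 4.5%]/[95.5%; 98.5%] or [2.3%; 5.7%]/[94.3%; 97.7%] or [3.1%; 6.9%]/[93.1%; 96.9"%]. The formula is that of one proportion from a simple random sample: "a two-sided 95.0 % confidence interval for a single proportion using the large sample normal approximation will extend 0.015 or 0.017 or 0.019". The same text stands in the Synopsis. Neither place mentions dentists, an ICC or a design effect.

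Sections 6.1 and 6.3.1 expect about 526 patients (500 evaluable) from about 100 private practices. Under 6.3.2 each participating dentist "should have included up to 6 patients who meet inclusion criteria", and sections 4 and 5.1 take these as the most recent consecutive uses.

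On identification, section 13.3 states that "the CRFs will be documented and evaluated without any identification attribute (no patient number, no site number"). Section 8.2 says that the CRFs and overview page "will be collected at dentist practice level and send in the enclosed envelope by mail to the CRO", without the sender's name or address.

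Section 11.3 promises suitable 95% confidence intervals, calls all analyses exploratory and leaves the detail to a separate SAP, which is not at hand.

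**The concern.** The primary outcome (section 11.2.1) is compliance with the SmPC on patient age, type of intervention, local anaesthetic product and dose, and OraVerse dose. Most of these are choices of the treating dentist, and section 7 places the application under that dentist's sole responsibility. Patients of one dentist are therefore likely to resemble each other, and 500 such patients carry less information than 500 independent ones.

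The survey's main statistical output is a proportion with its confidence interval, requested during the European approval procedure and described in the risk management plan (section 3.2). If the correlation is ignored, that proportion will look more precise than it is.

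This is not only a matter for the SAP. The SAP can choose an interval method, but it cannot recover a grouping that was never recorded. Once the envelopes are opened and the CRFs mixed, the grouping is lost.

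**Working it through.** **Inputs from the protocol.** Evaluable patients n = 500 (6.1, 11.4); non-adherence p = 3%, 4% or 5% (11.4); two-sided 95%, z = 1.96; about 100 dentists (6.3.1); at most 6 patients per dentist (6.3.2). Average evaluable cluster size m = 500/100 = 5.

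**Assumption.** The documents give no ICC. A range of 0.05 to 0.30 is used for illustration.

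**Step 1: the plan's own figures.** Half-width = 1.96 × √(p(1 − p)/500).
- p = 3%: 1.96 × √(0.03 × 0.97/500) = 0.01495
- p = 4%: 1.96 × √(0.04 × 0.96/500) = 0.01718
- p = 5%: 1.96 × √(0.05 × 0.95/500) = 0.01910

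These round to the stated 0.015, 0.017 and 0.019. The arithmetic is right; the independence assumption is what does not fit the design.

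**Step 2: with clustering.** DEFF = 1 + (m − 1) × ICC = 1 + 4 × ICC; effective n = 500/DEFF; half-width = step 1 × √DEFF.

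| ICC (assumed) | DEFF | Effective n | Half-width at 3% | at 4% | at 5% |
|---|---|---|---|---|---|
| 0 (as stated) | 1.0 | 500 | 1.50 | 1.72 | 1.91 |
| 0.05 | 1.2 | 417 | 1.64 | 1.88 | 2.09 |
| 0.10 | 1.4 | 357 | 1.77 | 2.03 | 2.26 |
| 0.20 | 1.8 | 278 | 2.01 | 2.30 | 2.56 |
| 0.30 | 2.2 | 227 | 2.22 | 2.55 | 2.83 |

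Half-widths are in percentage points. The widening is √1.2 = 1.10 to √2.2 = 1.48, that is 10% to 48%.

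**Step 3: what is possible without a cluster code.** Estimating the ICC, or using a cluster-robust or GEE variance, requires knowing which CRFs share a dentist. Under 13.3 that is not recorded. Two routes remain: assume an ICC, or take the worst case of 6 per dentist with ICC 1. The worst case gives DEFF = 1 + 5 × 1 = 6, effective n = 500/6 = 83, and half-widths of 3.66, 4.21 and 4.68 points. That is conservative, but too wide to be of much use.

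**The case against.** **The missing site number does not rule out every valid interval.** A reader might infer from 13.3 that no valid interval can be computed. That goes too far. Step 3 gives conservative intervals that need no site number. Section 8.2 also has the documents collected per practice and mailed in an envelope, so the grouping physically reaches the CRO and is lost only because 13.3 bars recording it.

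**Section 11.3 does not fix the plain normal-approximation (Wald) interval for the analysis.** That formula appears only in the sample-size justification; section 11.3 promises suitable intervals and defers to the SAP. It would be wrong to say that the planned analysis has a known coverage failure.

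**Coverage figures for that interval mix two effects.** In a beta-binomial simulation with 100 clusters of 5 and p = 3%, the unadjusted Wald interval covers about 90%, 87%, 82% and 78% at ICC 0.05, 0.1, 0.2 and 0.3. With fully independent patients it already covers only about 92%, because the normal approximation is poor at low proportions. An unadjusted exact interval still covers roughly 95% at ICC 0.05 and 93% at 0.10. The clustering effect does not vanish, however: at ICC 0.2 the exact interval falls to about 89%, and the Wilson interval goes from 95% at ICC 0 to about 86%.

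**The ICC is unknown and may be small.** Patient age, and a dose that depends on age and weight class, vary between patients of the same dentist. At ICC 0.05 to 0.10 the half-width at 3% rises only from 1.5 to between 1.6 and 1.8 points.

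**The stakes are limited.** The analyses are exploratory, and the protocol sets no hypothesis, threshold or decision rule. The omission of identifiers is deliberate and is the stated ground for needing no informed consent.

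These arguments limit the size and severity of the point. They do not answer its core: section 11.4 takes no account of the clusters fixed in 6.3, and 13.3 removes the means of measuring their effect.

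**Conclusion.** The point holds in this limited form. The half-widths of 1.5, 1.7 and 1.9 points are those of 500 independent patients and are too favourable for any positive within-dentist correlation. Under an assumed ICC of 0.05 to 0.30 with 5 evaluable patients per dentist, they become 1.6 to 2.2 points at 3% and 2.1 to 2.8 points at 5%. As long as no site or envelope code is recorded, the design effect cannot be estimated, and only an assumed ICC or the maximum-cluster bound is available.

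The size rests on the assumed ICC and on clusters of about equal size; the direction rests only on the ICC being positive. This should be fixed, but it is not critical: the analyses are exploratory and the variance formula does not alter the estimated proportion.

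**What to change.** - **Section 11.4 and the Synopsis:** restate the half-widths with a design effect over a range of assumed ICC, for example as in the table above, and say that the ICC is an assumption.
- **Sections 8.2 and 13.3:** let the CRO, on opening each envelope, put one random code on the overview page and all CRFs in it. The code is generated on receipt and linked to no name or address, so backtracking stays impossible. The wording in 13.3 must then allow it.
- **Section 11.3:** specify a cluster-adjusted interval suited to small proportions, for example a Wilson or exact interval on the effective sample size (500 divided by the estimated design effect). A cluster-robust Wald interval alone is not enough: in the simulation described above it covers only about 89% to 93% at p = 3% for ICC 0.05 to 0.5.

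The cost is a few sentences, a small extra step at the CRO and an adjustment of the anonymity wording. No more patients are needed if the wider intervals are accepted, but the stated precision becomes less favourable. The code must be in place before the first envelope is opened.

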11.5 Interim analysis

No interim analysis is planned.

12. TASKS AND RESPONSIBILITIES

12.1 Responsibilities of the expert

The expert will be involved in the preparation and approval of the protocol and its amendment(s).

12.2 Responsibilities of the Dentists

The Dentist will collect the data in accordance with this protocol.

It is the Dentist's responsibility to fill in the CRF and to record all data pertinent to the investigation. She/he will ensure that the information reported in the CRF is precise and accurate.

12.3 Responsibilities of Sanofi

Sanofi is responsible for taking all reasonable steps and providing adequate resources to ensure the proper conduct of the study.

13. ETHICAL, REGULATORY AND ADMINISTRATIVE RULES

13.1 Ethical principles

This is an anonymous retrospective retrolective cross-sectional drug utilisation survey. Therefore an assessment by an ethics committee is not necessary.

13.2 Laws and regulations

This study will be conducted in accordance with the guidelines for Good Pharmacoepidemiological Practice5 and the guidelines for Good Epidemiological Practice6 and the ENCePP Guide on Methodological Standards7.

13.3 Data protection

As defined and described in the RISK MANAGEMENT PLAN for Oraverse®, data collection will be completely anonymous. No backtracking will be possible, since the CRFs will be documented and evaluated without any identification attribute (no patient number, no site number). Therefore no informed consent of the patient is necessary.

13.4 Secrecy agreement

All material, information (oral or written) and unpublished documentation provided to the Dentist (or any action carried out by the company on their behalf), including the present protocol and the CRF, are exclusive property of the Company.

These materials or information (both global and partial) cannot be given or disclosed by the Dentist or by any person of her/his group to unauthorized persons without the prior formal written consent of the Company. The Dentist shall consider as confidential all the information received, acquired or deduced during the study and will take all necessary steps to ensure that there is no break of confidentiality, other than for information to be disclosed by law.

13.5 Record retention

The dentist shall arrange for the retention of study documentation until the end of the study. In addition the dentist will comply with specific local regulations/recommendations with regards to patient record retention.

It is recommended that the Dentist retains the study documents at least five years (5) after the completion or discontinuation of the study, unless otherwise specified in the Dentist Agreement in line with additional standards and/or local laws.

However, applicable regulatory requirements should be taken into account in the event that a longer period is required.

13.6 Discontinuation of the study

The Company can decide at any time and for any reason to discontinue the study; the decision will be communicated in writing to the participating Dentist and to the local regulations.

If appropriate, according to local regulations, Ethic Committee(s) (IRB/IEC) and Competent Authorities should be informed.

14. DOCUMENTATION AND USE OF THE STUDY RESULTS

14.1 Ownership and use of data and study results

No use of the data will be possible without the authorization of the Company conducting the study.

14.2 Publications

It is planned to communicate the results of the ORADUS study to the participating dentists.

It is planned to publish the results of the ORADUS study in a peer review journal based on the study report. Possible authors are all those matching the STROBE-initiative8 requirements and who have been implicated in:

- the design, data collection and analysis or interpretation of the data
- writing the manuscript or who significantly contributed to its review
- finalizing the manuscript.

If necessary a publication committee can be set up upon needs. Its main mission could be:

- to define the overall publication plan including the primary publications reporting new scientific findings/data from the study
- to review and approve (or abstain) all other publications proposals and drafts manuscripts regarding subsequent publications

